**Table 1 Schedule of Assessments (Screening through Day 25)**

Study Procedure	(Screening) a		Investigational Product Administration Period							Post-Treatment Evaluations
	1 st Episode	Retreatment (recurrent AMR) within 180 days	Day 1 a	Day 3	Day 5	Day 7	Day 9	Day 11	Day 13	

k If sucrose-free IVIg is administered on the same day as the screening visit, blood samples for immunogenicity should be obtained both prior to and after sucrose-free IVIg administration. Subjects where anti-C1 INH antibodies are detected will be followed until negative.

l DSA antibody will be determined by central and local laboratory analysis at screening (for initial or recurrent episode of AMR), and only by the central laboratory at all other time points specified. DSA testing may be performed locally at other time points after screening for all clinical assessments as part of standard of care. Additional serum may be collected by the central laboratory for future antibody and titer testing.

m Subjects will have a minimum of 5 plasmapheresis, plasma exchange, or immune adsorption treatments each followed by sucrose-free IVIg from the time of diagnostic biopsy for qualifying episode of acute AMR through Study Day 13. Plasmapheresis, plasma exchange, or immune adsorption treatments and sucrose-free IVIg may be provided as part of standard of care prior to study entry. Protocol-mandated plasmapheresis, plasma exchange, or immune adsorption treatments should be completed by Day 13. Additional DSA reduction treatments or doses of sucrose-free IVIg may be administered at the discretion of the investigator as part of standard of care.

n A total of 7 doses of investigational product will be administered: an initial IV infusion of 5000 U CINRYZE or placebo on Day 1, followed by 2500 U of CINRYZE or placebo IV on Days 3, 5, 7, 9, 11, and 13. If plasmapheresis, plasma exchange, or immune adsorption treatments therapy occurs on the same day as investigational product dosing, investigational product will be administered after completion of the DSA reduction therapy session and administration of sucrose-free IVIg.

o All medications (and selected blood products) taken from the day of the first dose of investigational product (Day 1) through the day of the last dose of investigational product (Day 13) will be recorded. In addition, medications used to treat AEs, SAEs, and adverse events of special interest (AESI) from time of informed consent through 30 days after the last dose of investigational product for each treatment period will also be recorded.

p The following medications will be collected for the duration of the study: Any IV steroids, Rituximab, Muromonab-CD3, Alemtuzumab, Anti-thymocyte globulin (rabbit), Lymphocyte immune globulin, anti-thymocyte globulin (equine), any IV immunoglobulin preparation, Daclizumab or basiliximab. See Section 5.5 of the protocol for additional medications to record.

q Adverse events and SAEs will be recorded from the time of Informed Consent through 30 days after the last dose of investigational product regardless of relationship to study treatment. Following the 30-day capture period for all AEs and SAEs, only AE/SAEs deemed related to investigational product or other protocol-mandated procedures, as well as the following AESIs regardless of relationship to investigational product: any hypersensitivity reaction, any thrombotic or thromboembolic event, any new episode of kidney allograft rejection (excluding AMR) even if the event does not qualify for retreatment with investigational product, and any kidney allograft failure, will be collected during the long-term follow-up phase of the study.

r Renal allograft function will be assessed by eGFRMDRD. Allograft failure and need for splenectomy will be assessed at all timepoints.

s Clinical chemistry includes BUN and serum creatinine

**Table 2 Schedule of Assessments (Month 3 through Month 48 [End of Study])a**

Study Procedure	Post-Treatment Evaluations									EOS/Month 48 or at patient discontinuation if after Month 6 (±28 days) b
	Month 3 (±21 days) b	Month 6 (±21 days) b	Month 12 (±21 days) b	Month 18 (±28 days) b	Month 24 (±28 days) b	Month 30 (±28 days) b	Month 36 (±28 days) b	Month 42 (±28 days) b	Early Discontinuation Visit Between Day 13 & Month 6	
Presence/absence of diabetes		✓								✓
Body Weight	✓	✓	✓	✓	✓	✓	✓	✓	✓	✓
BUN & Serum Cr with eGFR (both central and local lab) c	✓	✓	✓	✓	✓	✓	✓	✓	✓	✓
Central lab Proteinuria: Spot urine protein, urine Cr and urine protein/urine creatinine ratio	✓	✓	✓	✓	✓	✓	✓	✓	✓	✓
Kidney allograft biopsy & submission of pathology slides & images d		✓							✓	
Central lab Immunogenicity (anti-C1 INH antibodies)	✓	✓	✓ e		✓ e					
Central lab DSA identification f	✓	✓	✓	✓	✓	✓	✓	✓	✓	✓
Concomitant medications g	✓	✓	✓	✓	✓	✓	✓	✓	✓	✓
Adverse event monitoring h	✓	✓	✓	✓	✓	✓	✓	✓	✓	✓
Renal allograft assessment	✓	✓	✓	✓	✓	✓	✓	✓	✓	✓
Subject survival status	✓	✓	✓	✓	✓	✓	✓	✓	✓	✓
EQ-5D-5L	✓	✓	✓	✓	✓	✓	✓	✓		✓
Health Resource Utilization	✓	✓	✓	✓	✓	✓	✓	✓		✓

BUN=blood urea nitrogen; C1 INH=C1 inhibitor; Cr=creatinine; DSA=donor-specific antibody; eGFRMDRD=estimated glomerular filtration rate calculated by the Modification of Diet in Renal Disease; EOS=End of Study Visit; EQ-5D-5L= EuroQoL Group 5-Dimension 5-Level Self-report Questionnaire; SAE=serious adverse event; TG=transplant glomerulopathy

a The duration of the study will be event driven, and is based upon an assumption that there will be approximately 51 all-cause graft failures including death. The trial will continue until 51 such events are accrued and adjudicated by the independent, blinded nephrology EAC. See Section 9.5.1 of the protocol for additional details. However the maximum amount of time each subject will be followed in the study will be 4 years post initial treatment with investigational product. Subjects will complete visits every 6 months until the study is ended. If the study is stopped prior to the last enrolled subject completing Month 48, all subjects who have not reached Month 48 will be asked to return to the investigational site for their End of Study (EOS) visit.

**Table 2 Schedule of Assessments (Month 3 through Month 48 [End of Study])a**

Study Procedure	Post-Treatment Evaluations								
	Month 3 (±21 days) b	Month 6 (±21 days) b	Month 12 (±21 days) b	Month 18 (±28 days) b	Month 24 (±28 days) b	Month 30 (±28 days) b	Month 36 (±28 days) b	Month 42 (±28 days) b	Early Discontinuation Visit Between Day 13 & Month 6

b Visit dates for each visit from Month 3 through EOS will reference back to Day 1 of study entry and will be based on calendar months. Visit windows for each visit in [Table 2](#) will be ±21 days for Months 3, 6, and 12. Visit windows will be ±28 days for Months 18, 24, 30, 36, 42, 48, Early Discontinuation, and End of Study (EOS).

c In addition to Central laboratory testing, the local laboratory must obtain BUN, and creatinine values and calculate eGFR values for documentation in CRFs for each of the time points indicated as well as pre-AMR and resolution of AMR for all AMR episodes. Subjects who discontinue before 6 months should complete the Early Discontinuation Visit Between Day 13 & Month 6.

d In the event of discontinuation of a fully-dosed subject prior to the Month 6 Visit, every attempt will be made to obtain a biopsy at discontinuation to send to the independent, blinded pathology EAC for determination of TG. The required slides and images for the Screening, Month 6, early discontinuation before Month 6 (if applicable), and any other unscheduled standard of care biopsies, must be submitted to the Sponsor's designee within 30 days after the biopsy procedure, for subsequent submission to the EAC for review.

e Subjects where anti-C1 INH antibodies are detected will be followed to measure titers. At Months 12, 18, 24, 36, and 48 the test will be performed ONLY if anti-C1 INH antibodies are detected at the previous time point. At Month 3 and Month 6 the test will be performed in each patient.

f DSA antibody analysis will be performed by the central laboratory and will not be reported back to the investigator. Additional DSA testing at these and other time points may be performed by the local laboratory for all clinical assessments as part of standard of care. Additional serum may be collected for the central laboratory for future antibody and titer testing.

g For the duration of the study, the following concomitant/post-treatment medications will be collected in the case report form: Any IV steroids, Rituximab, Muromonab-CD3, Alemtuzumab, anti-thymocyte globulin (rabbit), lymphocyte immune globulin, anti-thymocyte globulin (equine), any IV immunoglobulin preparation, Daclizumab or basiliximab. In addition, medications used to treat any related AEs/SAEs or AESIs will also be recorded for the duration of the study as well as those listed in Section 5.5 of the protocol

h Adverse events and SAEs will be collected from the time of Informed Consent through 30 days after the last dose of investigational product regardless of relationship to study treatment. Following the 30-day capture period for all AEs and SAEs, only AE/SAEs deemed related to investigational product or other protocol-mandated procedures as well as the following AESIs regardless of relationship to investigational product: any hypersensitivity reaction, any thrombotic or thromboembolic event, any new episode of kidney allograft rejection (excluding AMR) even if the event does not qualify for retreatment with investigational product, and any kidney allograft failure will be collected during the long-term follow-up phase of the study.

**Table 3: Blood Sample Collection Time Points for Pharmacokinetic/ Pharmacodynamic Testing (All Subjects)**

Sample Day and Time	C1 INH (antigen and function), C3a, and C5a
Day 1: Prior to start of DSA reduction therapy, if performed, on Day 1	X
Day 1: Prior to Day 1 investigational product infusion (within 15 min)	X
Day 1: 1 h (+ 5 min) after start of Day 1 investigational product infusion	X
Day 7: Prior to start of DSA reduction therapy, if performed, on Day 7	X
Day 7: Prior to Day 7 investigational product infusion (within 15 min)	X
Day 7: 1 h (+ 5 min) after start of Day 7 investigational product infusion	X
Day 13: Prior to start of DSA reduction therapy, if performed, on Day 13	X
Day 13: Prior to Day 13 investigational product infusion (within 15 min)	X
Day 13: 1 h (+ 5 min) after start of Day 13 investigational product infusion	X

C1 INH=C1 inhibitor; C3a= anaphylatoxin split product of C3 activation important in chemotaxis; C5a=anaphylatoxin split product of C5 activation important for histamine release and chemotaxis; DSA=donor-specific antibody.

## 2.5 Determination of Sample Size

A total of 112 subjects (56 CINRYZE, 56 Placebo) will be randomized in a 1:1 ratio into 2 treatment groups: CINRYZE or placebo. Sample size was calculated for the primary endpoint and the key secondary endpoint using nQuery Advisor 7.0.

The primary endpoint in the study is the proportion of subjects with new or worsening TG at 6 months after treatment initiation. A 43% absolute difference in TG at 6 months between treatment groups (3/7 in placebo and 0/7 in CINRYZE) was observed in a subset of subjects (14/18) in the completed randomized Phase 2 pilot study (0624-201). For this study, the assumed proportion of subjects with new or worsening TG at 6 months will be 50% in the placebo group and 10% in the CINRYZE group. A sample size of 60 subjects (30 in placebo and 30 in CINRYZE) would be needed to obtain at least 90% power to detect a significant treatment difference at an alpha level of 0.025 (1-sided test).

The key secondary endpoint in the study is the proportion of subjects with all-cause graft failure. Assuming the proportions of subjects with graft failure due to AMR are 64% and 25% for placebo and CINRYZE, respectively, and all-other-cause graft failure rate is 12% for both placebo and CINRYZE, then the proportions of subjects with all-cause graft failure are 68% and 34% for placebo and CINRYZE, respectively. A total of 100 subjects will provide 90% power to detect an absolute treatment difference of 34% at an alpha level of 0.025 (1-sided test) for all-cause graft failure. These assumptions are based on literature ([Haririan et al. 2009](#); [Sharif et al. 2014](#); [OPTN/STRT Annual Data Report 2012](#)). Considering a 10% drop-out rate during the study, 112 subjects will be randomized to the study. Under these assumptions, the expectation is that there will be approximately 34 all-cause graft failures on placebo and approximately 17 all-cause graft failures on CINRYZE, giving 51 events total. The trial will continue until 51 such events are accrued and adjudicated by the nephrology EAC unless stopped prematurely based on findings at an interim analysis or until the final subject enrolled has been followed for 4 years post initial treatment with investigational product.

Additional eligible subjects may be enrolled based on the interim data analysis of the first 30 subjects who complete the Month 6 TG assessment for the re-estimation of sample size.

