9.8 Efficacy Analyses

9.8.1 Primary Efficacy Endpoint

The primary efficacy endpoint is defined as the proportion of subjects with new or worsening TG at 6 months post-treatment as determined by Banff criteria. The FAS set is the primary set for efficacy analysis. Subjects who do not have the primary efficacy endpoint assessed at 6 months post-dose will be assigned as failures.

The primary endpoint will be presented as the proportion of subjects with new or worsening TG occurring at 6 months post-treatment, and their difference between treatments ($\Delta_{Cinryze-Placebo}$) is defined as follows:

$$\Delta_{Cinryze-Placebo} = \Pi_{Cinryze} - \Pi_{Placebo}$$

Where $\Pi_{Cinryze}$ is the proportion of new or worsening TG at 6 months post-treatment in the CINRYZE group and $\Pi_{Placebo}$ is the proportion of new or worsening TG at 6 months post-treatment in the placebo group.

The analysis will employ a type I error rate of 0.025 (1-sided test) to test null hypothesis:

$$H_0 : \Pi_{Cinryze} - \Pi_{Placebo} \geq 0$$

Against the 1-sided alternative:

$$H_a : \Pi_{Cinryze} - \Pi_{Placebo} < 0$$

In the initial plan, the statistical difference between treatments will be evaluated by the CHW weighted test statistic Z_{CHW} when the first 60 subjects complete the assessments for the primary endpoint (second interim analysis). If the $Z_{CHW} \geq Z_{0.0249}$ (equivalent to p-value from the test is ≤ 0.0249 [1-sided test]), it will be concluded that CINRYZE is efficacious based on the proportion of subjects with new or worsening TG at 6 months after initiation of treatment and the result will serve as evidence of efficacy based on these 60 subjects. However, the number of subjects might be changed (increased) depending on the results of the first interim analysis in which the sample size will be re-estimated (Section 9.5.1).

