The purpose of the first interim analysis is to allow early stopping of the study for futility, assessing safety of the treatment, and potentially adjusting the sample size. The trial may be stopped for futility at the interim analysis or the sample size of the study may be adjusted up to ensure enough power to detect the treatment effect (section 14). The first interim analysis is planned to be performed when 30 subjects complete (half of the pre-defined sample size for primary endpoint, 15 subjects for each treatment group) the Month 6 visit. A fraction of alpha (0.0001) will be spent at the first interim analysis and accounted for in the overall type I error rate. Even if the value of test-statistics exceeds the efficacy boundary, the trial will not be stopped for efficacy. NOTE: For simplicity, 30 subjects complete the Month 6 visit and balanced arms are assumed to demonstrate statistical analyses in this document.

The futility of the study at the first interim analysis will be determined by calculating the conditional power (CP) based on observed trend at interim.

If the CP is  $< CP_{min}$ , the study will be stopped for futility. If the CP is between  $CP_{min}$  and 60%, the sample size will be adjusted up to make CP equal to 60%. The  $CP_{min}$  is the pre-specified lower limit of conditional power and will be specified in the DMC SAP before the 1st interim analysis. The analysis based on the adjusted number of subjects will be used for the final analysis on primary endpoint (i.e. second interim analysis in the study). The study will continue with the original planned sample size if CP is 60% or above.

The CP at the first interim analysis, assuming that the data that will be observed after the first interim analysis will follow the same distribution as seen at interim and the CHW weighted test statistic  $Z_{CHW}$  (Cui et al., 1999) as the final test statistic for second interim analysis (also see definition below), will be determined by the following formulae:

$$CP = P\left(Z_2 > \frac{Z_{1-\alpha} - w_1 Z_1}{w_2}\right)$$

$$= 1 - \Phi \left( \frac{Z_{1-\alpha} - w_1 Z_1 - \frac{\Delta}{\sqrt{\frac{2\bar{P}(1-\bar{P})}{n_2}}}}{w_2} \right)$$

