Where  $Z_1$  and  $Z_2$  are the Z test statistics from the first interim stage (from beginning to first interim analysis) and second interim stage (from first interim analysis to second interim analysis) respectively,  $w_1 = w_2 = \sqrt{\frac{1}{2}}$ ,  $n_2$  is the sample size at the second interim stage per treatment group,  $\Phi(\cdot)$  is cumulative standard normal distribution function,  $\Delta = \hat{\Pi}_{Placebo} - \hat{\Pi}_{Cinryze}$ , and  $Z_i$  ( $i = 1, 2$ ) is calculated as below:

$$Z_i = \frac{\hat{\Pi}_{Placebo} - \hat{\Pi}_{Cinryze}}{\sqrt{\bar{P}(1-\bar{P})\left(\frac{1}{n_{i,Placebo}} + \frac{1}{n_{i,Cinryze}}\right)}}$$

$\hat{\Pi}_{Placebo}$  and  $\hat{\Pi}_{Cinryze}$  are estimated proportions of new or worsening TG at 6 months post treatment at the first interim stage for the Placebo group and CINRYZE group, respectively.

The pooled proportion  $\bar{P} = \frac{n_{i,Placebo}\hat{\Pi}_{Placebo} + n_{i,Cinryze}\hat{\Pi}_{Cinryze}}{n_{i,Placebo} + n_{i,Cinryze}}$ , where  $n_{i,Placebo}$ ,  $n_{i,Cinryze}$  ( $i = 1, 2$ ) are numbers of subjects for the Placebo group and the CINRYZE group at first or second interim stage, respectively. The pre-defined sample size for second interim stage is:

$$n_{2,Placebo} = n_{2,Cinryze} = n_2 = 15$$

If  $CP(n_2 = 15) < CP_{min}$ , the futility of the study will be claimed.

If  $CP_{min} \leq CP(n_2 = 15) < 60\%$ ,  $n_2$  will be adjusted to  $n_2^*$  satisfy  $CP(n_2^*) \geq 60\%$ .

If  $CP(n_2 = 15) \geq 60\%$ , study will continue without sample size adjustment.

The second interim analysis serves as the final analysis for the primary endpoint. The purpose of the second interim analysis is to allow early stopping of the study for futility or for claiming of efficacy based on new or worsening TG at 6 months. This analysis will be done using the FAS when a required number of subjects (based on the sample size adjustment of first interim analysis) complete the Month 6 TG assessments. If the result of the final analysis for primary endpoint analysis is statistically significant at 0.0249, the primary null hypothesis will be rejected. The difference between treatments will be evaluated by using the CHW weighted test

statistic (Cui et al., 1999). The test statistic  $Z_{CHW}$  at the second interim analysis for TG will be derived based on CHW method, i.e.,

$$Z_{CHW} = \sqrt{\frac{15}{30}}Z_1 + \sqrt{\frac{15}{30}}Z_2 \quad (\text{Formulae 1})$$

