where  $Z_1$  is the normalized test statistic at first interim stage, and  $Z_2$  is the normalized test statistic for incremental sample size  $n_2^*$  for second interim stage after the sample size adjustment. If the number of TG events exceeds 5 for all four cells in the contingency table of treatment versus TG event,  $Z_i$  ( $i = 1, 2$ ) will be obtained using normal approximation, otherwise  $Z_i$  ( $i = 1, 2$ ) will be calculated from p-value of Fisher's Exact test as (Lechmacher et al., 1999):

$$Z_i = \Phi^{-1}(1 - p_i)$$

where  $\Phi^{-1}(.)$  is the function to return a quantile from the standard normal distribution,  $p_1$  is the p-value from Fisher's Exact test for the first interim stage, and  $p_2$  is the p-value from Fisher's Exact test for incremental sample size  $n_2^*$  for second interim stage after the sample size adjustment.

If  $Z_{CHW} \geq Z_{1-\alpha/2, 49}$  (equivalent to the p-value from the test  $\leq 0.0249$ ), the null hypothesis will be rejected. Otherwise, the futility of the study will be claimed.

The following sensitivity analyses will be conducted for TG assessment by the granular score for the FAS and then TG assessment by the standard score and the granular score for Per-Protocol Analysis Set-1:

- Sensitivity analysis 1: Primary analysis will be repeated based on Month 6 TG assessment by granular score for the Full Analysis Set
- Sensitivity analysis 2: Primary analysis will be repeated based on Month 6 TG assessment by standard score for the Per Protocol Analysis Set-1
- Sensitivity analysis 3: Primary analysis will be repeated based on Month 6 TG assessment by granular score for the Per Protocol Analysis Set-1

The TG assessment by the granular score at 6 months is defined as the following:

- Worsening TG is defined as an increase of 6.25 in the glomerular capillary double contour percentage between qualifying biopsy and 6-month biopsy.

- New TG is defined by granular Banff (based on 2013 Banff criteria) cg 0 score in the qualifying biopsy and granular Banff (based on 2013 Banff criteria) cg score of greater than 0 in the 6-month biopsy.

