In order to demonstrate the stability of the primary analysis method, sensitivity analyses will be performed at the point of final analysis of primary endpoint (i.e. second interim analysis for study) by using multiple imputation (MI) assuming missing at random (MAR) to assign missing endpoint and/or combined with Cochran–Mantel–Haenszel (CMH) test for treatment effect. The CMH model will assess the treatment effect controlling for (1) donor characteristic (living vs deceased), (2) baseline AMR severity (severe vs mild to moderate) and possibly (3) time to onset of qualifying AMR from current transplant (>100 days vs  $\leq$ 100 days) if degree of freedom allows. Sensitivity analyses defined below will be based on the FAS.

	Statistical Test	Logic to assign the missing TG assessment at 6 months
Primary analysis model	Fisher's Exact with CHW weighted test	If no TG assessment at 6 months, assign as failure.
Sensitivity analysis 4	Fisher's Exact with CHW weighted test	If no TG assessment at 6 months, perform MI.
Sensitivity analysis 5	CMH with CHW weighted test	If no TG assessment at 6 months, assign as failure.
Sensitivity analysis 6	CMH with CHW weighted test	If no TG assessment at 6 months, perform MI

For multiple imputation, a monotone missing pattern will be assumed and logistic regression model will be utilized. The imputation seed will be 83789524 and number of imputations will be set as 100. The logistic regression model may contain the following factors (descending order by importance) to impute the missing TG assessment at 6 months:

- (1) Treatment group (CINRYZE vs placebo);
- (2) AMR severity at baseline (severe vs mild/ moderate);
- (3) Donor characteristics (living donor vs deceased donor);
- (4) Normalized eGFR change ( $\Delta_{eGFR}$ ).  $\Delta_{eGFR} = \frac{eGFR_{baseline} - eGFR_{last}}{T}$ , where   
 $eGFR_{baseline}$  is the last eGFR results prior to the first dose of investigational product,  $eGFR_{last}$  is the last eGFR result before or at Month 6 or early discontinuation visit, and T = (last eGFR assessment date – Date of first dose + 1)/30.25;
- (5) Resolution of qualifying AMR (Resolved by 6 months /early discontinuation vs unresolved by 6 months/early discontinuation);

(6) AMR free time in months, which defines as (date of Month 6 or early discontinuation visit – Date of first dose +1 – number of days with AMR)/30.25

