## 17. CHANGES TO ANALYSES SPECIFIED IN PROTOCOL

At the first interim, one primary analysis and three sensitivity analyses were conducted for the primary endpoint mentioned in DMC SAP v3.0 dated 06 March 2019. Results from the primary analysis and two sensitivity analyses suggested very large increase to the sample size making it impractical to continue the study. From the result of the other sensitivity analysis, DMC members recommended to terminate the study based on the futility criteria specified in SAP. It was sponsor's decision to discontinue the study for futility after 1st interim analysis and produce an abbreviated CSR. Due to this decision, final analysis will include selected tables, figures, and listings which can be found in [section 20](#). Simple summaries will be provided for the primary endpoint data and selected sensitivity analyses of the primary endpoint. Tables, figures, and listings presented by timepoint will contain information collected only up to the study termination date.

The followings are the changes from protocol amendment 4 dated 22 November 2017 and SAP.

- Subject demographic and baseline characteristics for Safety set will not be included.
- No sensitivity analyses will be done using ITT set.
- Per Protocol Analysis Set-2 will not be derived.
- Some Sensitivity analyses for primary efficacy endpoint will not be conducted.
- Key secondary and other secondary efficacy analyses will not be conducted.
- Exploratory efficacy analyses will not be conducted.
- Measurement of healthcare resource utilization (HRU) will not be included.

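### SAP 2.5 states at least 90% power at 60 subjects, but the primary test in SAP 10.1 (stage-wise Fisher's exact combined by CHW) has 85.1%

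*SAP*

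**What the plan says.** SAP 2.5 gives the primary-endpoint sample size: "A sample size of 60 subjects (30 in placebo and 30 in CINRYZE) would be needed to obtain at least 90% power", assuming TG rates of 50% on placebo and 10% on CINRYZE and a one-sided alpha of 0.025. It names nQuery Advisor 7.0 as the software. It names no test and does not mention stages.

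SAP 10.1 defines the primary test:

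- The first interim is at 30 subjects, 15 per arm. "The pre-defined sample size for second interim stage is" also 15 per arm.
- Each stage yields its own Z. The normal approximation is used only if all four cells of the stage table exceed 5. Otherwise Z "will be calculated from p-value of Fisher's Exact test", as the normal quantile of 1 − p.
- The two Z values are combined with weights √(15/30) each, and the null is rejected at one-sided 0.0249.
- The table of analyses names the primary model as "Fisher's Exact with CHW weighted test".

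The same section provides for a sample size increase when conditional power lies between CPmin and 60%. CPmin "is the pre-specified lower limit of conditional power and will be specified in the DMC SAP before the" first interim analysis.

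Protocol 9.6 carries the same power sentence as SAP 2.5. Protocol 9.8.1 says only that "the statistical difference between treatments will be evaluated by the CHW weighted test statistic", without Fisher's test.

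**The concern.** A power statement should describe the test that will be run. Fisher's exact test is conservative in small tables because its p-values are discrete. SAP 10.1 applies it twice, to two tables of 15 per arm, so the loss occurs in both stages before the results are combined. A figure that fits one analysis of all 60 subjects need not carry over.

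What is at stake is the stated miss probability under the design assumption. It is not false-positive control, because the effect of discreteness is conservative.

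**Working it through.** **Inputs.** From SAP 2.5: rates 50% v 10%, 1:1 allocation, 60 subjects, alpha 0.025 one-sided. From SAP 10.1: stages of 15 + 15 per arm, the Fisher/normal switch, weights √(15/30), critical level 0.0249 (z = 1.9617). The SAP's Appendix 1 sample code takes a one-sided Fisher p-value.

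**1. Reproducing the stated figure.** For one comparison of 30 v 30 at one-sided 0.025:

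| Test | Power |
|---|---|
| Normal approximation | 94.3% |
| Fisher's exact, full enumeration | 91.4% |

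For the single Fisher test, 29 per arm is the smallest size that reaches 90% (90.02%). The statement of at least 90% is therefore sound arithmetic for a one-stage analysis.

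**2. The planned test.** For each stage, list all 16 × 16 outcomes (x events of 15 on placebo, y of 15 on CINRYZE) with their binomial probabilities. Set Zᵢ = Φ⁻¹(1 − pᵢ), where pᵢ is the one-sided Fisher p-value, or use the pooled normal Z if all four cells exceed 5. Reject if √½·Z₁ + √½·Z₂ ≥ 1.9617. Sum the probabilities over both stages:

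| Rule, 15 + 15 per arm | Power at 50% v 10% | Largest exact size |
|---|---|---|
| SAP 10.1 rule | 85.14% | 0.0087 |
| Fisher in both stages | 85.10% | 0.0069 |
| Mid-p Fisher in both stages | 93.4% | 0.0216 |
| Pooled normal Z in both stages | 95.1% | 0.0262 |

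A separate simulation of 400,000 trials agrees (power 85.1%). At the design rates the normal branch applies in only 0.16% of stages, so it cannot recover the loss. The exact size of the SAP rule at common rates of 10, 20, 30, 40 and 50% is 0.0011, 0.0044, 0.0062, 0.0076 and 0.0087, against a nominal 0.0249.

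**3. Sensitivity to reading.** Using alpha 0.025, cells of 5 or more, half the two-sided Fisher p-value, or Z = 0 when a stage p equals 1 gives 85.1% to 85.4%.

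**4. A worked example.** Take 14/30 v 5/30 in total, arising as 7/15 v 3/15 and then 7/15 v 2/15.

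- Stage 1: hypergeometric P(X ≥ 7 of 10 events on placebo) = 0.1225, so Z₁ = 1.162.
- Stage 2: P(X ≥ 7 of 9 events on placebo) = 0.0543, so Z₂ = 1.604.
- Combined: (1.162 + 1.604)/√2 = 1.956, p = 0.0252, which is above 0.0249 and so not significant.
- One Fisher test on 14/30 v 5/30: p = 0.0125, significant.

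**5. Size needed under the planned test.** With stage 1 at 15 per arm and the weights fixed, 18 per arm in stage 2 (66 subjects) gives 89.6%. At 19 per arm (30 + 2 × 19 = 68 subjects) it gives 90.8%.

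**6. Re-estimation.** This needs CPmin and a cap, which these documents do not give. Assume CPmin of 0 to 30% and a stage 2 cap of 41 to 150 per arm; 41 is what 112 randomised allow (112/2 − 15 = 41). The conditional power target is 60%. It is not settled whether Z₁ in the conditional power formula is the pooled normal or the Fisher version, so both are shown:

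| CPmin | Power, Z₁ normal | Power, Z₁ Fisher |
|---|---|---|
| 0% | 91.1–91.6% | 92.9–93.4% |
| 1% | 90.5–90.8% | 91.3–91.5% |
| 5% | 89.2–89.3% | 90.6–90.8% |
| 10% | 88.8–89.0% | 87.7–87.8% |
| 20% | 86.0% | 86.2–86.3% |
| 30% | 85.3% | 81.8% |

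Where power passes 90%, the average size is 65 to 80 subjects. Held to 60 subjects with the futility rule applied, power is 80% to 85%.

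**The case against.** The arithmetic is not in dispute. The case on the other side concerns weight and framing.

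- **The trial is over.** SAP 17 records: "It was sponsor's decision to discontinue the study for futility after" the first interim analysis. The second-stage test will not be run as planned. This stands, and it limits the point to the design record.
- **The design is not a fixed 60.** Conditional power between CPmin and 60% triggers an increase, and SAP 2.5 itself allows extra subjects, so whole-design power may exceed 90%. This is true for low CPmin. But the sentence is about 60 subjects, and any gain comes from enrolling more.
- **The Protocol has the same sentence.** Treating it as wrong in only one document may look uneven, since Protocol 9.5.1 defers the stage statistic to the interim SAP. But the Protocol does not specify Fisher's test, and CHW with pooled normal Z values has 95.1% power. The contradiction can be shown only within the SAP.
- **Overwriting the figure would hide how 60 was chosen.** This is a fair point. The correction should keep the basis of the original calculation visible.
- **85.1% assumes exactly 15 v 15 in each stage.** SAP 10.1 says balance is assumed for simplicity. The condition should be stated with the figure.

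**Conclusion.** The point holds. At 60 subjects, 15 per arm in each stage, and rates of 50% v 10%, the primary test in SAP 10.1 has exact power of 85.1%. That is about 5 points below the minimum stated in SAP 2.5, and the chance of missing the assumed effect is 14.9% rather than under 10%. The result does not depend on any contestable reading of the test rule.

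Over the re-estimation settings assumed in step 6, power runs from 82% to 93%. It passes 90% only at CPmin of 0–1% (Z₁ normal) or 0–5% (Z₁ Fisher), and only with more than 60 subjects on average. There is no type I error concern, and nothing here bears on whether the futility decision was right.

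**What to change.** In SAP 2.5, restate the power as about 85% for the Fisher/CHW test at 60 subjects (15 per arm per stage). Note that at least 90% corresponds to a single 30 v 30 comparison, and that re-estimation changes the figure depending on CPmin and any cap. The cost is one sentence and a less favourable stated figure.

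If the rule is reused in another trial, there are two options:

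- Keep the test and plan for 68 subjects, the first size to reach 90%.
- Compute each stage Z as the normal quantile of 1 minus the one-sided mid-p Fisher value, a wording change in SAP 10.1. This gives 93.4% at 15 + 15 with a maximum exact size of 0.0216. Size also stayed below 0.025 in the re-estimated designs checked (CPmin 0–30%, cap 41 or 80; maximum 0.0216) and for fixed stage 2 sizes of 15, 19, 26, 41, 60 and 80 per arm (maximum 0.0227). Other configurations would need their own check.

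Simply replacing Fisher with the pooled normal Z is not equivalent, because its exact size reaches 0.0262.
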